7.3.2 Human milk total thiamine concentration (4 weeks and 12 weeks)

Outcome:	Continuous outcome of total thiamine concentration ($\mu\text{g/L}$) in maternal human milk at 4 weeks and 12 weeks postpartum.
Primary analysis:	Fit a separate Emax curve for 4 and 12 weeks using nonlinear least squares model. Estimate of the dose that reaches 90% concentration (with 95% CI) at each timepoint will be reported.
Secondary analysis:	Fit a linear mixed effects model to outcome at 4, 12, and 24 weeks with treatment group, time, and treatment by time interaction as predictors. Treatment effects (difference in mean total concentration) will be estimated separately for each time point if the interaction p-value is <0.05 and for both time points combined otherwise.
Adjustment:	Health centre, human milk total thiamine at 2 weeks postnatal (linear mixed effects model only)

7.3.3 *Infant transketolase activity coefficient (24 weeks)*

- Outcome: Continuous outcome of infant transketolase coefficient (TKac) at 24 weeks postpartum.
- Primary analysis: Fit an Emax curve using nonlinear least squares approach. Estimate of the dose that reaches 90% concentration (with 95% CI) will be reported.
- Secondary analysis: Fit an Emax curve using nonlinear least squares approach allowing curve to vary by presence/absence of genetic hemoglobin disorder. Estimates of the dose that reaches 90% concentration by genetic hemoglobin disorder status will be reported following evidence from the global test.

7.3.4 *Maternal thiamine diphosphate concentration (24 weeks)*

- Outcome: Continuous outcome of maternal thiamine diphosphate concentration (ThDP; nmol/L) at 24 weeks postpartum.
- Primary analysis: Fit an Emax curve using nonlinear least squares approach. Estimate of the dose that reaches 90% concentration (with 95% CI) will be reported.
- Secondary analyses: First, fit an Emax curve using nonlinear least squares approach allowing curve to vary by presence/absence of genetic hemoglobin disorder. Estimates of the dose that reaches 90% concentration by genetic hemoglobin disorder status will be reported following evidence from the global test. Second, test for a treatment effect using linear regression and estimate a difference in mean concentration. Third, test for a treatment effect using linear regression with treatment group and treatment by genetic hemoglobin disorder interaction. Treatment effects (difference in mean concentration) will be estimated separately by genetic hemoglobin disorder where the relevant interaction term has a p-value <0.05. Pairwise comparisons will be reported following evidence of a treatment group effect (see Section 5.8). Fourth, test for a linear relationship using linear mixed effects model with CRP at 2 and 24 weeks postnatal, time and treatment group as predictors. Estimate of the mean change (with 95% CI) in ThDP for one unit increase in CRP will be reported. Fifth, test for a linear relationship using linear mixed effects model with AGP at 2 and 24 weeks postpartum, time and treatment group as predictors. Estimate of the mean change (with 95% CI) in ThDP for one unit increase in AGP will be reported.
- Adjustment: Maternal ThDP at 2 weeks postpartum, health centre (linear regressions and mixed effects models only)

7.3.5 *Maternal transketolase activity coefficient (24 weeks)*

- Outcome: Continuous outcome of maternal TKac at 24 weeks postpartum.
- Primary analysis: Fit an Emax curve using nonlinear least squares approach. Estimate of the dose that reaches 90% concentration (with 95% CI) will be reported.

- Secondary analyses: First, fit an Emax curve using nonlinear least squares approach allowing curve to vary by presence/absence of genetic hemoglobin disorder. Estimates of the dose that reaches 90% concentration by genetic hemoglobin disorder status will be reported following evidence from the global test. Second, test for a treatment effect using linear regression and estimate a difference in mean TKac. Third, test for a treatment effect using linear regression with treatment group and treatment by genetic hemoglobin disorder interaction. Treatment effects (difference in mean TKac) will be estimated separately by genetic hemoglobin disorder where the relevant interaction term has a p-value <0.05.
- Adjustment: Maternal TKac at 2 weeks postpartum, health centre (linear regressions only)

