5. To estimate the dose on the dose response curve where additional maternal intake of thiamine (oral dose) no longer meaningfully increases maternal ETKac at 24 weeks postpartum, and assess whether this depends on the presence/absence of a genetic hemoglobin disorder.
6. To test for differences between the 4 randomised groups on human milk total thiamine at 4, 12, and 24 weeks postpartum.
7. To test for differences between the 4 randomised groups on maternal ThDP at 24 weeks postpartum, and assess whether this depends on the presence/absence of genetic hemoglobin disorder.
8. To test for differences between the 4 randomised groups on maternal ETKac at 24 weeks postpartum and assess whether this depends on the presence/absence of a genetic hemoglobin disorder.
9. To estimate usual household salt intake from mean fortnightly salt disappearance (weight lost, in g).
10. To estimate salt intake among a subset of 100 lactating women, their male partners (if applicable), and their children 24-59 months (if applicable) using observed weighed salt intake records.
11. To estimate sodium intake using 24 hr urinary sodium concentrations among a subset of 100 lactating women.
12. To test for differences between the 0 & 10 mg randomised groups on Composite Mullen and the 5 subscales of the Mullen at 24 and 52 weeks postnatally.
13. To test for differences between the 0 & 10 mg randomised groups on Visual Paired Comparison Novelty Score and the attention and processing speed subscales at 24 and 52 weeks postnatally.

14. To test for differences between the 0 & 10 mg randomised groups on the Language Preference Task Score at 24 and 52 weeks postnatally.
15. To test for differences between 0 & 10 mg randomised groups on oculomotor scores at 24 and 52 weeks postnatally.
16. To determine the effect of inflammation, as measured by C-reactive protein (CRP) and α -1-acid-glycoprotein (AGP) on maternal ThDP at 2 and 24 weeks postpartum, and infant ThDP at 24 weeks postnatal.

5. Study Design

This will be a double-blind, four-parallel arm randomized controlled trial, in which 320 women and their newborn infants will be enrolled. Each dyad will participate in the study between 2 and 24 weeks postnatal, a 22-week intervention period. The primary outcome measure is human milk thiamine concentrations at 24 weeks postpartum (see **Figure 1**). There are additional cognitive assessments at 12 months (52 weeks) postnatal.

[figure not shown]

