2.2 Secondary Objectives

1. To estimate the dose on the dose-response curve where 90% of the maximum average is reached in the following outcomes:
 - a. Infant thiamine diphosphate concentrations (ThDP) at 24 weeks postnatal
 - b. Human milk total thiamine concentration at 4 and 12 weeks postpartum
 - c. Infant transketolase activity coefficient (TKac) at 24 weeks postnatal
 - d. Maternal ThDP at 24 weeks postpartum
 - e. Maternal TKac at 24 weeks postpartumand assess whether this depends on the presence/absence of genetic hemoglobin disorder for the following outcomes:
 - a. Infant ThDP at 24 weeks postnatal
 - b. Infant TKac at 24 weeks postnatal
 - c. Maternal ThDP at 24 weeks postpartum
 - d. Maternal TKac at 24 weeks postpartum
2. To test for differences between the 4 randomised groups on:
 - a. Human milk total thiamine at 4, 12, and 24 weeks postpartum
 - b. Maternal ThDP at 24 weeks postpartum
 - c. Maternal TKac at 24 weeks postpartum

and assess whether this depends on the presence/absence of genetic hemoglobin disorder for the following outcomes:

- a. Maternal ThDP at 24 weeks postpartum
- b. Maternal TKac at 24 weeks postpartum
3. To estimate the usual household salt intake from mean fortnightly salt disappearance (weight lost, in g).
4. In a subset of 100 lactating women, to estimate:
 - a. Salt intake of lactating women, their male partners (if applicable), and their children 24-59 months (if applicable) using observed weight salt intake records
 - b. Sodium intake using 24 hr urinary sodium concentrations in lactating women
5. To test for differences between the 0 mg and 10 mg treatment groups on the following outcomes at 24 and 52 weeks postpartum:
 - a. Composite and 5 subscales of Mullen
 - b. VPC Novelty score and the attention and processing speed subscales
 - c. Language Preference Task scores
 - d. Oculomotor scores
6. To determine the effect of inflammation, as measured by C-reactive protein (CRP) and α -1-acid glycoprotein (AGP) on the following outcomes:
 - a. Maternal ThDP at 2 and 24 weeks postpartum
 - b. Infant ThDP at 24 weeks postnatal

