7.2 Primary outcome variable

7.2.1 Human milk total thiamine concentration (24 weeks)

Outcome:	Continuous outcome of total thiamine concentration ($\mu\text{g/L}$) in maternal human milk at 24 weeks postpartum.
Analysis:	Fit an Emax curve using nonlinear least squares approach. Estimate of the dose that reaches 90% concentration (with 95% CI) will be reported.

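### SAP 7.3.2 gives milk thiamine group differences by visit only after a significant treatment-by-time test and otherwise pools an undefined pair of its three visits, so a secondary objective can go unanswered as stated

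*Combined protocol and SAP*

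**What the plan says.** Protocol section 4, secondary objective 6, reads: "To test for differences between the 4 randomised groups on human milk total thiamine at 4, 12, and 24 weeks postpartum". SAP 2.2 item 2a repeats it: "Human milk total thiamine at 4, 12, and 24 weeks postpartum".

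The analysis is the secondary analysis in SAP 7.3.2: "Fit a linear mixed effects model to outcome at 4, 12, and 24 weeks", with treatment group, time and their interaction as predictors, adjusted for health centre and milk thiamine at 2 weeks. The reporting rule is: "Treatment effects (difference in mean total concentration) will be estimated separately for each time point if the interaction p-value is" below 0.05, and "for both time points combined otherwise".

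Other analyses of the same outcome are dose-response only. For 24 weeks, SAP 7.2.1 fits an Emax curve: "Estimate of the dose that reaches 90% concentration (with 95% CI) will be reported". For the earlier visits, SAP 7.3.2 says: "Fit a separate Emax curve for 4 and 12 weeks using nonlinear least squares model". Neither yields differences in group means. Protocol section 11 plans mixed models for group comparisons without saying how visits are reported. SAP 5.8 gives a global test followed by Tukey comparisons over six pairs, and says nothing on visits.

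**The concern.** The objective names three visits, but the rule delivers visit-specific differences only when a 6-degree-of-freedom interaction test succeeds. Failure of that test may reflect low power as easily as constant effects. If effects truly are constant, the visit-specific results are withheld 95% of the time by construction.

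The fallback is also undefined. The model has three visits, while the section heading and outcome line name only 4 and 12 weeks.

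- If *both* means 4 and 12 weeks, a non-significant interaction leaves no group mean difference at 24 weeks anywhere in the plan.
- If it means all three visits, results after 2, 10 and 22 weeks of capsules are averaged (dosing starts at 2 weeks postpartum).

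SAP 3.5 says the analysts are unblinded during the analysis, so that choice would be made with allocation known.

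**Working it through.** **The plan's own figure first.** Inputs from SAP 3.6: difference 40 µg/L, SD 43, two-sided alpha 0.0083, power 90%, attrition 20%. With the noncentral t distribution the smallest adequate size is 38 per group (power 90.6%), and 38 / 0.8 = 47.5, rounded up to 48. The stated 48 reproduces. The normal approximation gives 36, and 36 / 0.8 = 45, which does not match.

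**Planning-curve effects.** SAP 3.6 simulates from a minimum of 136 to a maximum of 210 µg/L, a rise of 74. I read its 50% (at 1.2 mg) and 90% (at 2.4 mg) as shares of that rise, because 50% of 210 is 105, below the minimum. Then 2^h = 0.9 / 0.1 = 9, so h = 3.17. The effects over placebo are 37.0 at 1.2 mg, 66.6 at 2.4 mg and 73.9 at 10 mg.

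**Assumptions not in the documents.** 64 women per arm (80 less 20%); compound symmetry with within-woman correlation ρ of 0.3, 0.5 or 0.7; full effect at 12 and 24 weeks, and a fraction s of it at 4 weeks.

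**Power of the interaction test.** With 4 arms and 3 visits the test has 6 and 2 × (256 − 4) = 504 degrees of freedom and a critical F of 2.12. The noncentrality is

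λ = n × R / (SD² × (1 − ρ)), where R = (1 − s)² × (2/3) × Σ(effect − mean effect)².

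The sum over the four arms is about 3,390. For s = 0.8, R = 0.04 × 0.667 × 3,390 = 90.4. At ρ = 0.3, λ = 64 × 90.4 / (1,849 × 0.7) = 4.47, giving power 0.30.

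The three-visit pooled 10 mg versus placebo effect is 73.9 × (s + 2) / 3.

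| 4-week effect, share of later | Power at ρ = 0.3 / 0.5 / 0.7 | 4 weeks (µg/L) | Pooled (µg/L) | 24 weeks (µg/L) |
|---|---|---|---|---|
| 80% | 0.30 / 0.41 / 0.66 | 59.1 | 69.0 | 73.9 |
| 70% | 0.64 / 0.81 / 0.97 | 51.7 | 66.5 | 73.9 |
| 60% | 0.90 / 0.98 / >0.99 | 44.3 | 64.1 | 73.9 |

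If *both* means 4 and 12 weeks, the pooled value at 80% is (59.1 + 73.9) / 2 = 66.5.

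**A smaller effect.** Suppose the 10 mg effect is 20, 30 and 40 µg/L at the three visits, with the other arms at 0%, 50% and 90% of it. Power is then 0.41 / 0.56 / 0.82. The pooled value of 30 is 10 too low for week 24 and 10 too high for week 4. With 30, 36 and 40, power is 0.12 to 0.24.

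**Cost of visit-specific estimates.** Under compound symmetry and before baseline adjustment, the ratio of interval widths, single visit to pooled, is 1 / √((1 + 2ρ) / 3) = 1.37, 1.22 and 1.12 for ρ = 0.3, 0.5 and 0.7. If the 2-week value has the same correlation with later visits, adjusting for it gives √(3(1 − ρ²) / (1 − ρ² + 2(ρ − ρ²))) = 1.43, 1.34 and 1.28.

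Power at one visit for 40 µg/L: the standard error is 43 × √(2/64) = 7.60, and 40 / 7.60 = 5.26. Less the critical value 2.64, this leaves 2.62, so power is above 99% at alpha 0.0083.

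**The case against.** Gating on an interaction is a common convention. It is pre-specified here and does not conflict with protocol section 11. When the gate stays closed, a common effect is still tested and estimated, and if the response has levelled off by 4 weeks, pooling is unbiased and more precise.

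The error is also modest where the gate most often fails. In the 80% case the pooled value misses the 24-week effect by 73.9 − 69.0 = 4.9 µg/L: 7% of that effect, 12% of the 40 µg/L the SAP calls clinically meaningful, and less than the 7.6 µg/L standard error of one visit's contrast. At 4 weeks the miss is 69.0 − 59.1 = 9.9. On the planning-curve effects the gate opens more reliably as the change over time grows.

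Finally, reporting every visit means three global tests and up to 3 × 6 = 18 pairwise comparisons.

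All of this stands as a limit on the size of the problem, and the multiplicity needs an answer. It does not remove the mismatch: the objective names three visits, no other analysis supplies those differences, and *both* cannot describe three visits.

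**Conclusion.** The point holds for one secondary analysis. That the objective can go unanswered, and that the fallback is undefined, follow from the text alone. The size rests on the assumed time course and correlations: with a 4-week effect 80% of the later one, the gate opens in 30% to 66% of trials. At 60% or less it opens in at least 90%, given planning-curve effects; with smaller effects it can fail more often.

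A reader might infer two stronger things that the documents do not support.

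- **That the main result is at risk.** It is not. The primary outcome is the 24-week Emax dose, and the curves at 4 and 12 weeks are fitted separately without a gate.
- **That pooling will understate the 24-week effect.** Nothing in the documents says the milk response is still building at 4 weeks; that direction is an assumption.

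**What to change.** In SAP 7.3.2, always report model-based group differences with 95% confidence intervals at 4, 12 and 24 weeks from the treatment-by-time mixed model, whatever the interaction p-value, and give that p-value as description only. Apply the SAP 5.8 global test and Tukey comparisons within each visit. Either state that no adjustment is made across visits, in line with SAP 5.8 for secondary outcomes, or name one visit, such as 24 weeks, as the main comparison. If a pooled effect is kept, report it in addition and name its visits.

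The change is to wording only, with the same model and data. The price is wider intervals than a pooled estimate would give (12% to 37% before baseline adjustment) and more comparisons. Power at each visit remains ample on the plan's own inputs.

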7.3.6 Household salt intake

- Outcome: Continuous outcome of total salt consumption (g) in one day.
- Primary analysis: Descriptive means and standard deviation (overall and by number of individuals in the household) of total salt consumption within a day in a subset of 100 households.
- Secondary analysis: Descriptive means and standard deviation of the difference in salt intake, and intraclass correlation coefficient, between two days in a subset of 75 households.

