8.2 Eligibility criteria

All women must provide written informed consent to participate. Participants must meet the following criteria:

- mothers of a newborn
- aged 18-45 years
- most recent pregnancy was normal (i.e. no known chronic conditions, preeclampsia, gestational diabetes etc.), and the singleton infant was born without complications (e.g. low birth weight (<2.5 kg), tongue tie, cleft palate)
- intends to exclusively breastfeed for six months
- resides in Kampong Thom province, Cambodia, and is not planning to move in the next six months
- is not currently taking, and hasn't taken any thiamine-containing supplements over the previous 4 months
- is not currently participating in any nutrition programs beyond normal care
- is willing to consume one capsule daily from 2 weeks through 24 weeks postpartum
- is willing for her entire household consume only salt provided by the study team
- is willing for the following biological samples to be collected: a maternal venous blood sample and human milk sample at 2 weeks postpartum, a human milk sample at 4 and 12 weeks postpartum, and maternal and infant blood samples and a human milk sample at 24 weeks postpartum

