9.2 Fortnightly monitoring

Every two weeks between 2-24 weeks, a member of the research team will visit the participant in her home to distribute new blister packs and collect used blister packs (compliance measure). At this time the field staff will also ask a small number of questions about capsule compliance, selling or sharing of salt, and about infant and young child feeding (IYCF) practices (was the infant exclusively breastfed over the previous two weeks). The field staff will weigh the household salt container to assess salt disappearance, and will provide more salt to the household.

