9.3 Salt disappearance

At the initial home visit after randomization, field staff will check that the household has removed all salt from the home, and will distribute table salt in specialized study containers. Using calibrated scales (sensitive to 1 g), field staff will log the initial weight of the salt container(s). Participants will be asked to consume only salt provided by the study, and since Cambodian families eat from a common pot, they will be instructed for all family meals to be prepared using this salt. At each fortnightly monitoring visit, field staff will weigh the salt container(s) to determine household salt consumption from salt disappearance. In addition, field staff will ask women to confirm the household members eating from the common pot.

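### SAP 7.3.6 groups household salt by an undefined head count and leaves unused the records of who eats from the common pot and of salt sold or shared

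*Combined protocol and SAP*

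**What the plan says.** **Objective.** SAP 2.2, objective 3 (protocol Section 4, secondary objective 9) is "To estimate the usual household salt intake from mean fortnightly salt disappearance (weight lost, in g"). The unit is the household and the measure is the fall in container weight.

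**Analysis.** SAP 7.3.6 defines the outcome as "Continuous outcome of total salt consumption (g) in one day". The planned summary is "Descriptive means and standard deviation (overall and by number of individuals in the household) of total salt consumption within a day", for 100 households, with a between-day comparison in 75 of them. The SAP does not say who counts as an individual in the household, and it plans no figure per head or per eater from this total.

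**Data collected.** Protocol 9.3 describes the fortnightly container weighing and adds that "field staff will ask women to confirm the household members eating from the common pot". Protocol 9.2 has staff ask at each fortnightly visit a "small number of questions about capsule compliance, selling or sharing of salt", and whether the infant was exclusively breastfed over the preceding fortnight. The SAP gives no use to the common-pot record or to the answers on selling and sharing.

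**Population.** Under protocol 8.2 every mother "intends to exclusively breastfeed for six months". Each household therefore starts with at least one member who is not expected to eat the study salt.

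**Purpose.** Protocol 3.7 gives the overall aim as obtaining what is needed to formulate a thiamine-fortified salt, and names usual salt intake as one of the inputs. Protocol 9.3 says the intake data are needed to calculate dosages.

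**The concern.** A fortification level depends on how much salt reaches each person who eats it. A table of household totals by household size invites the reader to divide one by the other, more so because the background figure in protocol 3.6 is per capita (15 g/day). If the count includes members who eat none of the salt, that division gives too low a figure. The trial already records the better denominator.

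The question on selling and sharing matters in a different way and needs no division. When intake is defined as weight lost, salt that leaves the house is scored as eaten. Staff ask about this at every visit, but the plan has no rule for acting on the answer.

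**Working it through.** The documents state no household size, number of eaters or salt per eater, so there is no figure of the plan's own to reproduce.

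**1. Does the grouping bias a planned estimate?** The outcome is a household total S. The overall mean and SD of S do not involve household size N, so they are unaffected. Within the table, suppose every household has exactly one non-eater, the infant. N and N − 1 then correspond one to one, and each row holds the same households under a label that is one too high. Rows mix households with different numbers of eaters only where the number of non-eaters varies, for example where some members regularly eat elsewhere.

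**2. What happens if the table is read per person?** With k non-eaters among N members, salt per eater is S/(N − k). Dividing by all members gives S/N. The ratio is (N − k)/N, an understatement of k/N.

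For k = 1 (infant only; N is assumed):

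| N | Understatement, 1/N |
|---|---|
| 3 | 33.3% |
| 4 | 25.0% |
| 5 | 20.0% |
| 6 | 16.7% |
| 7 | 14.3% |
| 8 | 12.5% |

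Illustration at N = 5, with 15 g/day taken per eater purely for scale: S = 4 × 15 = 60 g; 60/5 = 12 g; 12/15 = 0.80, so 20% low. With two non-eaters it is 2/5 = 40% low.

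The direction assumes that nobody outside the household eats from the pot. With the infant as the only non-eater and v regular visitors, the number of eaters is N − 1 + v. At N = 5, one visitor brings the error to zero, and two make S/N 20% too high (6/5 − 1).

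**3. Salt sold or shared.** Let U be the salt eaten by the household per fortnight, f the fraction of fortnights with salt sold or shared, and g the grams that leave on each such occasion. Mean weight lost is U + f × g, so intake is overstated by f × g / U. The direction is upward whenever f and g exceed zero. None of f, g or U is given, so the size cannot be calculated from the documents.

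**4. Which data does 7.3.6 use?** Set side by side, the sections do not match:

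- Objective 3 calls for fortnightly disappearance. Protocol 9.2 and 9.3 have the container weighed every fortnight from 2 to 24 weeks, with no restriction to a subset.
- SAP 7.3.6 analyses a one-day total in 100 households, with 75 repeated. Those numbers match the observed weighed-intake sub-study in protocol 9.3, which records only 1 to 3 individuals per household and so does not by itself yield a household total.

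If 7.3.6 is meant to use container weights, the selling and sharing problem applies to it, but the one-day outcome and the subset are unexplained. If it is meant to use observed intake, that problem does not arise there, but the SAP then has no analysis of objective 3.

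**The case against.** The strongest reply is that the plan promises no intake per eater from this table. Protocol 9.3 itself says that disappearance data cannot support strong estimates of how salt is divided within a household, and for that reason adds observed weighed intakes and urinary sodium, analysed in SAP 7.3.7 and 7.3.8. The head count is undefined rather than wrong, and an analyst could implement it as the common-pot members. Exclusive breastfeeding is an intention at entry, not a certainty.

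Most of this stands, and it rules out the stronger reading. A reader might infer that the trial will understate salt per eater by 14% to 25% (households of seven down to four). The documents do not support that: the percentages arise only if someone divides a total by household size. A reader might also put a number on sold or shared salt. For example, four eaters at 15 g/day use 15 × 4 × 14 = 840 g per fortnight, and 500 g given away in 5% to 15% of fortnights would add 3% to 9%. The 500 g, the frequencies and the four eaters are all invented, and 15 g/day is a per capita figure, so this is not a finding either. Nor would a rule that excludes fortnights fit a one-day outcome as 7.3.6 now stands.

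Two things survive the reply. SAP 7.3.7 covers only the mother, her male partner and a child of 24 to 59 months, so any other eaters appear only in the household total. And a count that could be implemented in two ways should be defined, particularly when the more relevant one is already collected.

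**Conclusion.** The concern holds in a limited form. SAP 7.3.6 groups by an undefined count and leaves unused two items that bear directly on interpreting household salt. The grouping itself biases no planned mean or SD. A per-person reading would be too low by 1/N per non-eater: 12.5% to 33.3% for assumed household sizes of eight down to three, with the infant the only non-eater and no visitors at the pot. Under the weight-lost definition in objective 3, salt sold or shared is counted as eaten; the direction is clear but the amount is unknown.

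This is a descriptive secondary outcome and does not touch the primary analysis. The change is still worth making, because household salt use is meant to inform a fortification level and the change requires no new data item.

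**What to change.** 1. In SAP 7.3.6, replace the head count with the number of household members recorded as eating from the common pot, and state that the study infant counts only if so recorded.
2. Add grams per eater per day. For container data this is weight lost, net of salt added, divided by days between weighings and by the number of eaters. Present it as a household average, not as any individual's intake.
3. Reconcile 7.3.6 with objective 3. Specify the fortnightly disappearance estimate that the objective calls for. If the one-day total in 100 households is kept, state how it is obtained and which visit's common-pot record applies to it.
4. For the fortnightly estimate, report results with and without fortnights in which salt was reported sold or shared, together with how many fortnights and households are affected.

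The protocol already has staff ask both questions, so this is a change of SAP wording with no added visit or participant burden. The downside is small: the sensitivity analysis loses some fortnights, possibly selectively, since households that share salt may differ from those that do not. For that reason it should sit beside the full-data estimate and not replace it.
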